10.6.3 BREAKING THE STUDY BLIND/PARTICIPANT CODE

Breaking of blind will occur to [name] and [name] in the case of severe physical AEs (e.g., VTE) or psychiatric AEs (hospitalization/suicide attempt).

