5.5 PREMATURE TERMINATION OR SUSPENSION OF STUDY

Administration of study agent will be halted when three serious AEs* determined to be "probably related" (i.e., with new onset during study patches/pills) are observed. The PI will immediately notify the DSMB when this occurs. The DSMB will notify the study sponsor and investigators immediately when the third severe event is reported and enrollment screens will stop accepting new study participants. The DSMB will request the statistical analyses and tables that they wish to review, and these will be prepared by an unblinded biostatistician associated with the study. All requested documentation will be provided to the DSMB. The DSMB will convene an ad hoc meeting by teleconference or in writing as soon as possible. The DSMB will provide recommendations for proceeding with or terminating the study to the PI and the NIH. The study sponsor will inform all appropriate regulatory agencies of the temporary halt and the disposition of the study (i.e., terminate, continue).

*Statistically, the most likely examples of serious adverse events in the present study include development of a venous thromboembolism or a suicide attempt during an experimental phase of the study.

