6.1.8 DOSE ADJUSTMENTS/MODIFICATIONS/DELAYS

If the PI determines that a participant must be discontinued from the protocol (see Section 5.4.2), The PI and [name] will be unblinded via IDS. If the participant was on active E2/P4, [name] will supervise the subject's discontinuation of E2/P4. Regardless of the condition the participant was in, the PI and [name] will continue to follow the participant until resolution via appropriate clinical care (e.g., hospitalization for suicidality).

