8 ASSESSMENT OF SAFETY

The safety of the study and its participants (as described in 2.3.1) will be monitored via (1) Supervising physician [name]./Ph.D. (hormone-related AEs) and [name]. (mood and suicide-related AEs) as well as (2) a Data and Safety Monitoring Board (DSMB).

AEs will be assessed daily during the telephone contacts in the two administration conditions, and will be assessed weekly at laboratory visits. All AEs will be reported immediately to the PI and [name], who will determine severity and next steps.

A DSMB of three experts outside the PI's department will evaluate AEs that are submitted during scheduled reviews (every 6 months). The DSMB will be composed of MDs and PhDs from relevant disciplines, including clinical psychology, gynecology, and endocrinology.

Although not expected given the doses and duration of hormone exposure, the DSMB will, during scheduled reviews, specifically evaluate the frequency of AEs related to the hormonal RCT. The DSMB will specify the tables and data it wishes to have presented to it at all meetings, including but not limited to, moderate to severe side effects and all serious adverse events. **DSMB review of this study will occur every six months**. At these meetings the DSMB will also review data from participants who have been discontinued by study staff or who have withdrawn or dropped out of the study, and the reasons for discontinuation. The DSMB will also identify if any study procedures should be altered or stopped in the event of an indication of harm to participants attributable to the study interventions. The DSMB will evaluate issues of participant safety as well as the adequacy and integrity of accumulating data, review of enrollment data, and making recommendations regarding safety.

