8.2.2 RELATIONSHIP TO STUDY AGENT

For all AEs, [name] will urgently collaborate with [name] to determine the AE's causality based on temporal relationship and clinical judgment. The degree of certainty about causality will be graded using the categories below.

Definitely Related – There is clear evidence to suggest a causal relationship, and other possible contributing factors can be ruled out. The clinical event occurs in a plausible time relationship to drug administration and cannot be explained by concurrent disease or other drugs or chemicals. The response to withdrawal of the drug (dechallenge) should be clinically plausible. The event must be pharmacologically or phenomenologically definitive, with use of a satisfactory rechallenge procedure if necessary.

Probably Related – There is evidence to suggest a causal relationship, and the influence of other factors is unlikely. The clinical event occurs within a reasonable time after administration of the drug, is unlikely to be attributed to concurrent disease or other drugs or chemicals, and

CLEAR 2 Study Protocol: Hormones and Suicide Risk, Version 9, 07-02-2020, Page 38 of 64

follows a clinically reasonable response on withdrawal (dechallenge). Rechallenge information is not required to fulfill this definition.

Possibly Related – There is some evidence to suggest a causal relationship (e.g., the event occurred within a reasonable time after administration of the trial medication). However, other factors may have contributed to the event (e.g., the participant's clinical condition, other concomitant events). Although an AE may rate only as "possibly related" soon after discovery, it can be flagged as requiring more information and later be upgraded to "probably related" or "definitely related," as appropriate.

Unlikely to be related – A clinical event whose temporal relationship to drug administration makes a causal relationship improbable (e.g., theevent did not occur within a reasonable time after administration of the trial medication) and inwhich other drugs or chemicals or underlying disease provides plausible explanations (e.g., theparticipant's clinical condition, other concomitant treatments).

Not Related – The AE is completely independent of study drug administration, and/or evidenceexists that the event is definitely related to another etiology. There must be an alternative, definitive etiology documented by [name] or [name].

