8.5 STUDY HALTING RULES

Administration of study agent will be halted when three serious AEs* determined to be "probably related" (i.e., with new onset during study patches/pills) are observed. The PI will immediately notify the DSMB when this occurs. The DSMB will notify the study sponsor and investigators immediately when the third severe event is reported and enrollment screens will stop accepting new study participants. The DSMB will request the statistical analyses and tables that they wish to review, and these will be prepared by an unblinded biostatistician associated with the study. All requested documentation will be provided to the DSMB. The DSMB will convene an ad hoc meeting by teleconference or in writing as soon as possible. The DSMB will provide recommendations for proceeding with the study to the PI and the NIH. The study sponsor will inform all appropriate regulatory agencies of the temporary halt and the disposition of the study.

*Statistically, the most likely examples of serious adverse events in the present study include development of a venous thromboembolism or a suicide attempt during an experimental phase of the study.

CLEAR 2 Study Protocol: Hormones and Suicide Risk, Version 9, 07-02-2020, Page 41 of 64

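### Nothing requires relatedness of halting-rule SAEs to be graded before the blind is broken, and *probably related* has two conflicting meanings

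*Combined protocol and SAP*

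**What the plan says.** **Unblinding.** Section 10.6.3 has the blind broken to two people (names removed) "in the case of severe physical AEs (e.g., VTE) or psychiatric AEs (hospitalization/suicide attempt". Section 6.1.8 states that once the PI decides a participant must be discontinued, "The PI and [name] will be unblinded via IDS". Section 5.4.2 likewise pairs breaking the blind with discontinuation when severe mood symptoms or raised suicide risk emerge.

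**Grading.** Section 8 states: "All AEs will be reported immediately to the PI and [name], who will determine severity and next steps". Section 8.2.2 has two people (names removed) determine "causality based on temporal relationship and clinical judgment" on a five-level scale. For *probably related*, the event must, among other conditions, be one that "follows a clinically reasonable response on withdrawal (dechallenge". A grade of *possibly related* may be raised later as information arrives.

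**Halting rule.** Sections 5.5, 8.5 and 10.4.7.1 halt the study agent after "three serious AEs* determined to be" *probably related*, and explain that term in brackets: "i.e., with new onset during study patches/pills) are observed". They add that the likeliest SAEs "include development of a venous thromboembolism or a suicide attempt during an experimental phase of the study".

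**Order.** Section 10.6.1 keeps staff blinded and lets the pharmacy service (IDS) release codes only for safety. No section says whether the relatedness grade comes before or after release, and none names a blinded assessor.

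**The concern.** A causality grade that feeds a halting rule should be made without knowledge of the treatment. Here the events expected to count are also events that release the code, probably to the people who grade them. The 8.2.2 definitions turn on timing after drug administration and on the response to withdrawal. Learning that a participant was on placebo, progesterone or estradiol therefore bears directly on the grade.

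The team also holds a directional expectation. Section 3 predicts that progesterone will reduce suicide risk and that estradiol will be mildly protective. Section 2.3.1 describes a beneficial effect of active hormone in the preceding experiment. Knowing the code could move a grade in either direction. What is at stake is whether the three-event count reflects the events or the graders' knowledge of the condition. Expectedness (8.2.3) and the relatedness criterion for unanticipated problems (8.1.3) have the same gap.

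**Working it through.** The plan gives no operating characteristics for the halting rule, so there is no figure to reproduce. The check sets the sections against one another.

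1. **Do the events overlap?** Code-release events (10.6.3): severe physical AEs such as VTE, and psychiatric hospitalization or suicide attempt. Events expected to drive the halt (5.5, 8.5, 10.4.7.1): VTE and suicide attempt. Section 8.1.2 gives the same two as notable SAEs. Both expected halting events are on the code-release list.

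2. **Do the people overlap?** Section 6.1.8 unblinds the PI and one other person. Section 8 has the PI and one other person determine severity. Section 8.2.2 has two people grade causality. With names removed, it is probable but not confirmed that the graders are the people unblinded.

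3. **Is the order fixed?** No. Section 8 requires immediate reporting, 8.2.2 asks for urgent collaboration, and 6.1.8 places unblinding after the decision to discontinue. A blinded initial grade is compatible with all of these, but none requires one.

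4. **When can an 8.2.2 grade of *probably related* be completed?** The dechallenge condition can be judged only after dosing stops. If dosing stops through discontinuation, 5.4.2 and 6.1.8 break the blind. If it ends on schedule at day +21 (7.3.3), 10.6.3 still breaks the blind for these event types. A qualifying grade would therefore ordinarily be completed with the condition known. The allowance for later upgrades points the same way.

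5. **Which definition feeds the count?** Two are available:
   - The bracketed text in the halting rule asks only whether onset fell during study patches or pills. Placebo uses the same patch and pill schedule (4.1), so this test gives the same answer whatever the condition.
   - The 8.2.2 scale requires judgment of other causes and of dechallenge, and so is open to influence from the code.

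   The rule speaks of events *determined to be* probably related, and 8.2.2 is the only procedure for determining relatedness. The documents do not settle which definition governs.

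**The case against.** The strongest reply is the halting rule's own bracketed text. Read literally, every SAE with onset on patches or pills counts, and knowing the condition cannot change the total. That stands, and it limits the point to the 8.2.2 definition. It does not remove the point, because the two definitions conflict.

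Other safeguards exist. Deaths and immediately life-threatening events go to the sponsor within 24 hours whether related or not (8.4.2). Severe AEs go to the IRB and DSMB within one week with no relatedness filter (8.4.1). The DSMB reviews serious events every six months and can recommend changes or stopping (8). The halting count is not the only protection.

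Three stronger readings are tempting, and the documents do not support them:

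- *The graders have already been unblinded when they grade.* The order is unspecified, the names are removed, and section 8 divides hormone-related from mood-related events between two supervisors.
- *The DSMB's tables carry biased relatedness columns.* Section 10.4.4 tabulates AEs by whether they emerged during treatment, and section 8 lets the DSMB choose its tables. Neither mentions relatedness.
- *Unblinded grading roughly halves the rule's sensitivity.* Suppose each truly related SAE is graded so with probability p. The first three all count with probability p³: .9³ = .729 and .7³ = .343. Both values of p are assumed, and the rule is not confined to the first three events. With five such SAEs, P(at least 3 counted) = 10p³(1−p)² + 5p⁴(1−p) + p⁵, which is .99 at p = .9 and .84 at p = .7. Knowing that a participant was on active drug could also raise p.

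**Conclusion.** The point holds in limited form. For the events most likely to be counted, the plan releases the code without first requiring a recorded grade. Under the formal definition, a *probably related* grade would ordinarily be completed after release. Whether this reaches the halting count depends on which of two conflicting definitions applies: it can under 8.2.2, and it cannot under the timing text.

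This rests on one inference, that the graders and the unblinded people are the same. Sections 6.1.8, 8 and 8.2.2 make that probable. No numerical effect on the rule can be derived. The plan gives no SAE rate and no probability of a given grade, blinded or unblinded, and it reports no serious adverse events in the preceding study (2.1). The change should be made because it is cheap and removes an avoidable route for bias.

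**What to change.** - In 8.2.2 and 10.6.3, state that an initial grade of severity, relatedness and expectedness is recorded and time-stamped before IDS releases the code. State also that this must not delay any unblinding needed for care. Where unblinding cannot wait, flag the grade as made unblinded.
- Keep any later re-grade as a separate dated entry, and show the DSMB both.
- Reconcile the bracketed text in 5.5, 8.5 and 10.4.7.1 with 8.2.2, so that one stated definition, applied to the blinded entry, feeds the count. The reconciled text should say how an initial grade is handled when the dechallenge response is not yet known. Which definition to adopt is for the sponsor and the DSMB.
- Say by role who grades and who is unblinded.

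The three-event threshold is untouched. The cost is one extra form field and a few sentences. The downside is that some initial grades will be made with less information, which the dated re-grade allows for.

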11 SOURCE DOCUMENTS AND ACCESS TO SOURCE DATA/DOCUMENTS

All data collected in this study will be maintained on the UIC protected servers and in clinical binders kept under lock and key in [name] locked laboratory.

12 QUALITY ASSURANCE AND QUALITY CONTROL

QC procedures will be implemented beginning with the data entry system and data QC checks that will be run on the database will be generated; this will be carried out by study project manager [name]. Any missing data or data anomalies will be communicated to the PI for clarification/resolution.

Following written SOPs, the monitors will verify that the clinical trial is conducted and data are generated, documented (recorded), and reported in compliance with the protocol, GCP, and the applicable regulatory requirements (e.g., Good Laboratory Practices (GLP), Good Manufacturing Practices (GMP)).

The investigational site will provide direct access to all trial related sites, source data/documents, and reports for the purpose of monitoring and auditing by the sponsor, and inspection by local and regulatory authorities.

13 ETHICS/PROTECTION OF HUMAN SUBJECTS

CLEAR 2 Study Protocol: Hormones and Suicide Risk, Version 9, 07-02-2020, Page 47 of 64

13.1 ETHICAL STANDARD

The investigator will ensure that this study is conducted in full conformity with Regulations for the Protection of Human Subjects of Research codified in 45 CFR Part 46, 21 CFR Part 50, 21 CFR Part 56, and/or the ICH E6.

13.2 INSTITUTIONAL REVIEW BOARD

The protocol, informed consent form(s), recruitment materials, and all participant materials will be submitted to the IRB for review and approval. Approval of both the protocol and the consent form must be obtained before any participant is enrolled. Any amendment to the protocol will require review and approval by the IRB before the changes are implemented to the study. All changes to the consent form will be IRB approved; a determination will be made regarding whether previously consented participants need to be re-consented.

13.3 INFORMED CONSENT PROCESS

13.3.1 CONSENT/ASSENT AND OTHER INFORMATIONAL DOCUMENTS PROVIDED TO PARTICIPANTS

Consent forms describing in detail the study agent, study procedures, and risks are given to the participant and written documentation of informed consent is required prior to starting intervention/administering study product. The following consent materials are submitted with this protocol including the adult informed consent and the consent for storage of specimens.

13.3.2 CONSENT PROCEDURES AND DOCUMENTATION

Informed consent is a process that is initiated prior to the individual's agreeing to participate in the study and continues throughout the individual's study participation. Extensive discussion of risks and possible benefits of participation will be provided to the participants and their families. Consent forms will be IRB-approved and the participant will be asked to read and review the document. The investigator will explain the research study to the participant and answer any questions that may arise. All participants will receive a verbal explanation in terms suited to their comprehension of the purposes, procedures, and potential risks of the study and of their rights as research participants. Participants will have the opportunity to carefully review the written consent form and ask questions prior to signing. The participants will have the opportunity to discuss the study with family or health care providers and think about it prior to agreeing to participate. The participant will sign the informed consent document prior to any procedures being done specifically for the study. The participants may withdraw consent at any time throughout the course of the trial. A copy of the informed consent document will be given to the participants for their records. The rights and welfare of the participants will be protected by emphasizing to them that the quality of their medical care will not be adversely affected if they decline to participate in this study.

13.4 PARTICIPANT AND DATA CONFIDENTIALITY

CLEAR 2 Study Protocol: Hormones and Suicide Risk, Version 9, 07-02-2020, Page 48 of 64

Participant confidentiality is strictly held in trust by the participating investigators, their staff, and the sponsor(s) and their agents. This confidentiality is extended to cover testing of biological samples in addition to the clinical information relating to participants. Therefore, the study protocol, documentation, data, and all other information generated will be held in strict confidence. No information concerning the study or the data will be released to any unauthorized third party.

The study participant's contact information will be securely stored at each clinical site for internal use during the study. At the end of the study, all records will continue to be kept in a secure location for as long a period as dictated by local IRB and Institutional regulations.

Study participant research data, which is for purposes of statistical analysis and scientific reporting, will be transmitted to and stored on protected servers at UIC. Identifying information will be linked to ID number only in one password-protected file. Individual participants and their research data will otherwise be identified by a unique study identification number. The study data entry and study management systems used by study staff will be secured and password protected. At the end of the study, all study databases will be de-identified (linking files destroyed) and archived on UIC servers.

Certificate of Confidentiality

To further protect the privacy of study participants, a Certificate of Confidentiality will be obtained from the NIH. This certificate protects identifiable research information from forced disclosure. It allows the investigator and others who have access to research records to refuse to disclose identifying information on research participation in any civil, criminal, administrative, legislative, or other proceeding, whether at the federal, state, or local level. By protecting research participants, Certificates of Confidentiality help achieve the research objectives and promote participation in studies by helping assure confidentiality and privacy to participants.

13.4.1 RESEARCH USE OF STORED HUMAN SAMPLES, SPECIMENS OR DATA

Study data include blood samples from laboratory visits and all psychosocial data from study participation.

- Intended Use: Samples and data collected under this protocol may be used to study the role of E2, P4, ALLO, and inflammatory gene expression in suicidality and psychiatric symptoms.
- Storage: Access to stored samples will be limited using locked access areas. Samples and data will be stored using codes assigned by the investigators. Data will be kept in password-protected computers. Only investigators will have access to the samples and data.
- Tracking: Data will be tracked using password-protected files on the UIC server. Disposition at the completion of the study: All serum samples will be kept under locked access areas at UIC. Study participants who request destruction of samples will be notified of compliance with such request and all supporting details will be maintained for tracking.

CLEAR 2 Study Protocol: Hormones and Suicide Risk, Version 9, 07-02-2020, Page 49 of 64

13.5 FUTURE USE OF STORED SPECIMENS

Data collected for this study will be analyzed at UIC within 2 years of the time they are collected. The data and samples collected in this study will not be stored for future use, and will not be shared with other investigators.

14 DATA HANDLING AND RECORD KEEPING

14.1 DATA COLLECTION AND MANAGEMENT RESPONSIBILITIES

Data collection is the responsibility of the staff at the site under the supervision of the PI. The investigator is responsible for ensuring the accuracy, completeness, legibility, and timeliness of the data reported.

All source documents should be completed in a neat, legible manner to ensure accurate interpretation of data. Black ink is required to ensure clarity of reproduced copies. When making changes or corrections, cross out the original entry with a single line, and initial and date the change. DO NOT ERASE, OVERWRITE, OR USE CORRECTION FLUID OR TAPE ON THE ORIGINAL.

Copies of the electronic data will be provided for use as source documents and maintained for recording data for each participant enrolled in the study. Data reported in the electronic data file derived from source documents should be consistent with the source documents or the discrepancies should be explained and captured in a progress note and maintained in the participant's official electronic study record.

Clinical data (including AEs, concomitant medications, and expected adverse reactions data) and laboratory data will be entered into a local database on UIC servers. The data system includes password protection and internal quality checks, such as automatic range checks, to identify data that appear inconsistent, incomplete, or inaccurate. Clinical data will be entered directly from the source documents.

